6.4 Study Intervention Compliance

The administration of intravenous nivolumab will be performed in the clinic on D1 of every treatment cycle. The date and time of each infusion administered in the clinic will be recorded in the source documents and recorded in the electronic case report form (eCRF). Reasons for dose delay or infusion interruption will also be recorded in the source data and in the eCRF. The number of vials used will be recorded on the appropriate treatment dispensing form.

When participants are dosed at the site, they will receive regorafenib directly from the Investigator or designee.

Additionally, for treatment compliance oral administration of regorafenib will be done under supervision of site staff on PK visit days, and the dosing and time must be documented in the source data and eCRF on the following days: D1, D8 and D15 of C1, and on D1 and D15 of C2.

When participants self-administer regorafenib at home, compliance with regorafenib will be assessed at each study visit. Compliance will be assessed by counting returned tablets. A record of the number of regorafenib tablets dispensed to and returned by each participant must be maintained and reconciled with regorafenib start and stop dates, including dates for dose delays and/or dose reductions which will also be recorded in the eCRF. Any discrepancies between actual and expected amount of returned study medication must be discussed with the participant at the time of the visit, and any explanation must be documented in the source

records. An adequate record of receipt, distribution, and return/destruction of all study intervention must be kept.

CCI

CCI

CCI

CCI

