Skin toxicity grade (CTCAE)	Occurrence	Dose Interruption	Dose modification (when resuming treatment)
G1	Any	Maintain dose level and institute supportive measures immediately for symptomatic relief	No Change
G2	1 st occurrence	Interrupt therapy for a minimum of 7 days, until toxicity resolves to Grade 0–1	Institute supportive measures and continue same dose or consider decrease by 1 dose level
	No improvement within 7 d or 2 nd occurrence	Interrupt until toxicity resolves or improves to G1.	When resuming treatment, treat at reduced dose level or consider discontinuation ^a
	3 rd occurrence	Discontinue	
G3	1 st occurrence	Institute supportive measures immediately. Interrupt therapy for ≥ 7 d until toxicity resolves or improves to G1.	When resuming treatment, decrease by 1 dose level
	2 nd occurrence	Institute supportive measures immediately. Interrupt therapy for ≥ 7 d until toxicity resolves or improves to G1.	When resuming treatment, decrease by 1 additional dose level or consider discontinuation ^a
	3 rd occurrence	Discontinue	

Abbreviations: CTCAE = common terminology criteria for adverse events; G = Grade; HFSR = hand-foot skin reaction

- If reductions are required resulting in regorafenib daily dose of less than 80 mg every other day, the regorafenib will be permanently discontinued. If toxicity returns to Grade 0-1 after dose reduction, dose reescalation is permitted in the subsequent cycle at the Investigator's discretion. Subjects requiring a delay of >4 weeks should discontinue regorafenib treatment. However, continuation of regorafenib may be considered if, in the investigator's opinion, the patient may continue to benefit from the regorafenib treatment, and after consultation with Sponsor.

Table 6–5: Regorafenib Dose Modification Guidance, Non-Immune Toxicities: Hypertension

CTCAE Grade	Suggested regorafenib dose interruption	Suggested regorafenib dose modification
Specific guidance for HYPERTENSION		
G1	No change.	Consider increased BP monitoring
G2	If symptomatic, hold until symptoms resolve and diastolic BP \leq 90 mmHg. Treat with anti-hypertensive medications	At restart, continue at the same dose level
G3	Hold until diastolic BP \leq 90 mm Hg, and if symptomatic, until symptoms resolve. Treat with additional anti-hypertensive medications	At restart, continue at the same dose level.
	If BP is not controlled with the addition of new or more intensive therapy.	Reduce by 1 dose level

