8.3 Adverse Events and Serious Adverse Events

Progression per se should not be regarded as AE. Instead, the associated signs and symptoms should be recorded as AEs.

The intensity of AEs should be documented using the NCI-CTCAE, v5.0.

The study treatment action should be recorded separately for each study treatment as detailed in the eCRF.

- Drug withdrawn
- Drug interrupted
- Drug delayed
- Dose reduced
- Dose not changed
- Dose increased
- Not applicable
- Unknown

The definitions of an AE or SAE can be found in Section [10.3](#).

AEs will be reported by the participant (or, when appropriate, by a caregiver, surrogate, or the participant's legally authorized representative or health care professional not involved in the study).

The Investigator and any qualified designees are responsible for detecting, documenting, and recording events that meet the definition of an AE or SAE. They remain responsible for following up SAEs, or AEs, considered related to the study intervention or study procedures, or those that caused the participant to discontinue the study (see Section [7](#)).

Investigators should refer to the Safety Information section of the current IB of regorafenib and the current IB of nivolumab for the expected side effects. As with any agent, there is always the potential for unexpected AEs, including hypersensitivity reactions. The IB will be updated if any new relevant safety data are obtained.

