6.5.2 Adverse events

All adverse events (AE) whether considered drug-related or not, will be reported on the CRF with diagnosis, start/stop dates, dates of any grade change, action taken, whether treatment was discontinued, any corrective measures taken, and outcome. For all events, the relationship to treatment and the severity of the event will be determined by the Investigator. AEs will be classified and coded using the National Cancer Institute (NCI) Common Terminology Criteria Adverse Event (CTCAE), version 5.0 .

According to the protocol (See section 8.3.1 of the final study protocol) AE will be collected from the signing of the informed consent form (ICF) until the end of active FU visit, which should be 30 days after last dose of regorafenib and 100 days after last dose of nivolumab. An AE is considered as treatment-emergent (TEAE) if it starts during treatment or within the post-treatment time window.

For further definitions of the terms AE, SAE, seriousness, intensity, causal relationship with treatment, causal relationship to protocol-required procedures, action taken, and outcome please refer to the respective section of the protocol.

In the CRF only the worst action taken with regard to the study medication was captured, if nothing else changed while the AE was ongoing. Therefore all tables using this field, will have a footnote, mentioning this fact.

In addition to standard medDRA grouping, treatment-emergent AE of importance will be defined as follows:

- Rash grade 3 or higher. Rash consists of the following MedDRA LLT*:

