- Overview over treatment-emergent AEs leading to study drug withdrawal
- Treatment-emergent AEs leading to study drug withdrawal by worst CTCAE grade
- Treatment-emergent AEs leading to regorafenib dose reduction
- Treatment-emergent AEs leading to drug interruption
- Treatment-emergent AEs leading to dose reduction and/or drug interruption
- Treatment-emergent AEs of importance
- Overview over treatment-emergent drug-related AEs
- Treatment-emergent drug-related AEs with grades 3, 4, or 5
- Treatment-emergent drug-related AEs by worst CTCAE grade
- Treatment-emergent drug-related AEs occurring in at least 5% of patients
- Overview over treatment-emergent drug-related AEs leading to study drug withdrawal

- Treatment-emergent drug-related AEs leading to study drug withdrawal by worst CTCAE grade
- Treatment-emergent drug-related AEs leading to regorafenib dose reduction
- Treatment-emergent drug-related AEs leading to drug interruption
- Treatment-emergent drug-related AEs leading to dose reduction and/or drug interruption

The incidence of pre-treatment AE and non-treatment-emergent AEs during long-term follow-up will be tabulated. Other non-treatment-emergent AE will be presented by means of a subject data listing only.

Overview tables of adverse events will be presented in addition to the frequency tables.

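### The separate tables of AEs leading to drug interruption and to regorafenib dose reduction draw on a worst-action field that cannot hold both actions for one event, so their counts can be too low

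*SAP*

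**What the plan says.** SAP 6.5.2 describes the limit of the field itself: "In the CRF only the worst action taken with regard to the study medication was captured". The sentence carries a condition, namely that the worst action "was captured, if nothing else changed while the AE was ongoing". The stated handling is disclosure: "Therefore all tables using this field, will have a footnote, mentioning this fact". The same section says that each AE is reported with "dates of any grade change, action taken, whether treatment was discontinued", among other items.

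The table list in SAP 6.5.2 then has one table for "Treatment-emergent AEs leading to drug interruption", one for AEs leading to regorafenib dose reduction, and one for either or both. Drug-related versions of all three follow, and SAP 6.5.3 plans the same three for SAEs. All count patients, not events.

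Protocol 8.3 adds: "The study treatment action should be recorded separately for each study treatment as detailed in the eCRF". Its list of actions has separate entries for a drug that was interrupted and one that was delayed. Neither document ranks the actions.

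Protocol 6.6.1 gives the regorafenib rules. For Grade 3 hand-foot skin reaction, Table 6-4 says "Interrupt therapy for ≥ 7 d until toxicity resolves or improves to G1", and resumption is at a lower dose level. A further source exists: protocol 6.4 has regorafenib tablet counts reconciled with start and stop dates, "including dates for dose delays and/or dose reductions which will also be recorded in the eCRF". SAP 6.5.1 plans a summary of dose modification for each drug.

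**The concern.** A field that keeps one action per event cannot support separate incidences of two actions when the dosing rules often apply both to the same event. The event is filed under the later, more severe action and disappears from the table for the earlier one. Within an affected table the error goes one way: a count can be lost but not gained.

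The loss is also selective. Events mild enough to restart at the same dose remain as interruptions, while those needing a further step drop out. Protocol 9.4.5 promises a summary of AEs leading to treatment modification, and regorafenib is escalated within patients at cycle 2, so a reader will look to these tables for tolerability. Nothing here touches the primary analysis of response.

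**Working it through.** The documents state no figure on this point, so there is none to reproduce. The check has two parts: which tables lose which events, and an illustration of size on assumed rates.

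**How often the rules give one event more than one action**

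| Source | Course for one event |
|---|---|
| Table 6-3, Grade 4 first occurrence; Grade 3 third occurrence | hold, then reduce or consider stopping |
| Table 6-3, Grade 3 first and second occurrence | hold, then same dose or reduce |
| Table 6-4, Grade 3 hand-foot skin reaction, first occurrence | interrupt, then reduce |
| Table 6-4, Grade 2 hand-foot skin reaction, first occurrence | interrupt, then same dose or consider reducing |
| Table 6-5, Grade 2-3 hypertension | hold (Grade 2 only if symptomatic), normally same dose |
| Table 6-6, liver tests, first occurrence in the two categories that call for a delay | delay, then reduce (in the more severe category, only if restarting is judged worth the risk) |
| Protocol 6.6.2, nivolumab | delay or stop; never reduced |

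Hold-then-reduce is therefore a common course for regorafenib, but not a universal one. For nivolumab only delay-then-withdrawal can matter.

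**Which table loses the event**

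Let I = interruption, R = reduction, W = withdrawal. Take one AE record, keep only the worst action, and see which tables still count it. Because no ranking is given, both plausible orders are shown, with W worst in each.

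| True sequence | Stored if W>R>I | Lost from | Stored if W>I>R | Lost from |
|---|---|---|---|---|
| I only | I | none | I | none |
| R only | R | none | R | none |
| I then R | R | interruption | I | reduction |
| I then W | W | interruption, combined | W | interruption, combined |
| R then W | W | reduction, combined | W | reduction, combined |
| I, R, then W | W | all three | W | all three |

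A held-then-reduced record is lost from exactly one separate table and always stays in the combined one. The combined table loses only records that end in withdrawal, under either order.

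**Illustration of size (assumed rates)**

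The denominator of 70 treated patients is from SAP 5.1. Everything else is assumed: a share a of patients has an AE-led interruption; in a share s of those, every interrupting record ends in reduction; in a further share w, every one ends in withdrawal. The order is W>R>I and no record is split.

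- Interruption table shows 70 × a × (1 − s − w).
- Of these interrupted patients, the combined table shows 70 × a × (1 − w).

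With a = 0.5, the true count is 70 × 0.5 = 35:

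| s | w | Interruption table | Combined table |
|---|---|---|---|
| 0 | 0 | 35.0 | 35.0 |
| 0.25 | 0 | 35 × 0.75 = 26.25 | 35.0 |
| 0.5 | 0 | 35 × 0.5 = 17.5 | 35.0 |
| 0.75 | 0 | 35 × 0.25 = 8.75 | 35.0 |
| 0.5 | 0.1 | 35 × 0.4 = 14.0 | 35 × 0.9 = 31.5 |

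For a = 0.3 (21 patients) and a = 0.7 (49 patients), s = 0.5 with w = 0 gives 10.5 and 24.5. The output follows directly from the assumed s and w, so it shows the form of the error and does not estimate it.

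**The case against.** The strongest reply is the condition in the SAP sentence. Grade changes are dated, and many regorafenib holds last until the grade falls, so a grade change may come before the restart at a lower dose and open a record with its own action. If the CRF worked that way, many held-then-reduced events would be kept in both tables. This stands as a real limit: the documents do not say whether a grade change splits a record. Equally, an event that resolves completely before restart might leave no later record, and the SAP itself thought the loss real enough to footnote every table that uses the field.

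Other points also have weight:

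- Counting is per patient, so another AE whose worst action was interruption keeps that patient in the overall row. It does not protect rows for a single term, such as hand-foot syndrome, which SAP 6.5.2 names as an AE of importance.
- The planned interruption table is not limited to one drug, so a nivolumab delay for the same event may keep a patient in.
- SAP 6.5.1 already summarizes dose modification by drug. That is useful, but it is not said to be tied to AEs or to give the incidence of interruption.
- The limitation is disclosed. A footnote, however, does not let a reader recover the missing counts.

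A reader might infer that all three tables fail through hold-then-reduce, or that the safety report as a whole is tilted towards good tolerability. Neither follows. The combined table keeps those events, and a lost event is still counted under its more severe action, in the reduction or withdrawal tables. Nor do the documents show these tables feeding Phase III planning: the planned early look covers response data only (SAP 4.4).

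**Conclusion.** The point holds in a limited form. Unless separate records were opened, the separate interruption and reduction tables can only be too low. Hold-then-reduce affects one of them: the interruption table if reduction ranks worse, the reduction table if the order is reversed. Escalation to withdrawal affects the table for each earlier action and the combined table as well.

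The size is unknown. It depends on three things the documents do not give: the ranking, the record-splitting rule, and the share of events that moved on to a more severe action. It would be nil if every change of action had its own record. The documents do not support saying that every event handled under a hold-then-reduce rule is missing, or putting any particular percentage on the loss.

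These are descriptive safety tables, and the protocol's safety endpoint is AE incidence and severity, so this is a reporting defect and no threat to the trial's main conclusion. It is worth correcting because the SAP already recognizes the limit of the field and still plans separate incidences from it.

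**What to change.** In SAP 6.5.2 and 6.5.3:

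1. State the ranking used for the worst action, including where a delayed drug falls, and say whether a grade change opens a new record.
2. Replace the two separate tables by cumulative ones for each drug: *interruption/delay or a more severe action* and, for regorafenib, *reduction or withdrawal*. With withdrawal ranked above reduction and reduction above interruption, no event in the sequence table above is lost. If the CRF ranked interruption above reduction, the categories must be reversed to match.
3. Extend the combined table to *any modification including withdrawal*.
4. Under SAP 6.5.1, report patient-level incidence of interruption and reduction for each drug from the dosing eCRF dates, regardless of AE attribution.

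Deriving AE-specific interruptions by linking dosing dates to AEs is less safe. Protocol 6.4 mentions reasons for nivolumab delays but only dates for regorafenib, and linking a modification to every AE ongoing on that date could attribute it to coincident events.

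The cost is SAP wording and a little programming on data the protocol already collects. The drawback is that cumulative categories also count events that went straight to the more severe action, so the table titles must say so.

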6.6 Dose Modification

Based on the known toxicity profiles of regorafenib and nivolumab, certain AEs are likely to be associated with one drug versus the other. For example, treatment emergent hypertension and HFSR are likely to be associated with regorafenib rather than nivolumab; similarly,

immune-related AEs are likely to be associated with nivolumab rather than regorafenib. However, some drug-related AEs such as diarrhea, abnormal thyroid function, and fatigue are overlapping. Therefore, it is important to evaluate each AE to confirm etiology or exclude other causes in order to determine proper management of the adverse reaction and action regarding study treatment. A careful decision should be made by Investigators based on all clinical information, e.g., relatedness to study medications.

Dose modifications must be based on the maximum toxicity experienced during a cycle. If appropriate, the Investigator may attribute each toxicity event to regorafenib or nivolumab alone or to the combination. In situations where clear attribution cannot be made to individual drugs, more conservative dose modification approach should be used for both drugs. In case of dose modifications, any efforts should be made to restart study intervention as per original schedules for regorafenib and nivolumab.

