- Alternative causes, such as underlying disease(s), concomitant therapy, and other risk factors, as well as the temporal relationship of the event to study intervention administration will be considered and investigated.
- The Investigator will also consult the IBs and/or Product Informations, for marketed products, in his/her assessment.
- For each AE/SAE, the Investigator **must** document in the medical notes that he/she has reviewed the AE/SAE and has provided an assessment of causality for both, regorafenib and nivolumab.
- There may be situations in which an SAE has occurred and the Investigator has minimal information to include in the initial report to Bayer. However, **it is very important that the Investigator always make an assessment of causality for every event before the initial transmission of the SAE data to Bayer.**
- The Investigator may change his/her opinion of causality in light of FU information and send a SAE FU report with the updated causality assessment.
- The causality assessment is one of the criteria used when determining regulatory reporting requirements.
- Immune-mediated adverse events (IMAEs) are AEs consistent with an immune-mediated mechanism or immune-mediated component for which non-inflammatory etiologies (e.g., infection or tumor progression) have been ruled out. IMAEs can include events with an alternate etiology which were exacerbated by the induction of autoimmunity. Information supporting the assessment will be collected on the participant's eCRF.
- Every AE must be assessed by the investigator with regard to whether it is considered immune-mediated.

FU of AEs and SAEs

- The Investigator is obligated to perform or arrange for the conduct of supplemental measurements and/or evaluations as medically indicated or as requested by Bayer to elucidate the nature and/or causality of the AE or SAE as fully as possible. This may include additional laboratory tests or investigations, histopathological examinations, or consultation with other health care professionals.
- If a participant dies during participation in the study or during a recognized FU period, the Investigator should provide access to any post-mortem findings including histopathology
- New or updated information will be recorded in the originally completed eCRF.
- The Investigator will submit any updated SAE data to Bayer within 24 hr of receipt of the information.

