10037893, 10037894, 10005876, 10005877, 10012483, 10012884, 10013784, 10013785, 10058692, 10015138, 10015139, 10015143, 10015241, 10015242, 10015243, 10015244, 10015283, 10015285, 10015286, 10015585, 10015587, 10058694, 10058693, 10058721, 10015724, 10015725, 10016064, 10018081, 10018087, 10077181, 10018093, 10018094, 10018095, 10062432, 10062439, 10077163, 10062442, 10062443, 10049201, 10019117, 10024426, 10024437, 10079448, 10062704, 10079449, 10062705, 10025418, 10025422, 10049195, 10025423, 10025424, 10027022, 10027967, 10027968, 10027969, 10027970, 10028837, 10075807, 10074762, 10068748, 10033726, 10033727, 10033728, 10033729, 10033730, 10033737, 10033740, 10034120, 10054770, 10078918, 10074684, 10037844, 10037845, 10037872, 10048332, 10037848, 10037851, 10037855, 10048310, 10037856, 10037858, 10037863, 10037867, 10037868, 10037869, 10037870, 10037873, 10079349, 10037874, 10037875, 10037876, 10037878, 10037880, 10063646, 10066739, 10057984, 10037890, 10059872, 10038183, 10038186, 10038187, 10038188, 10081713, 10082785, 10080343, 10062880, 10040806, 10081571, 10040841, 10040913, 10081143, 10073477, 10047983, 10047984

- High Billirubin (if entered as AE)
- High Liver Enzymes (excluding GGT) (if entered as AE)
 - This table will be broken out by presence of liver metastases (yes vs. no) additionally
- Hand/Foot Syndrom, consisting of the following MedDRA LLT*:
10033552, 10033552, 10070580, 10069640, 10019111, 10048776, 10019126,
10063069, 10033553, 10054524, 10070580, 10069640, 10019111, 10048776,
10019126, 10063069, 10033553, 10054524

All tables for TEAE/TEAE, except the one displaying (S)AE by relationship, will also be broken out by relationship to drug (Rego/Novo/Both). Relationship to drug in this case is defined as:

- Related to Rego: relationship to regorafenib = yes AND relationship to nivolumab = no
- Related to Nivo: relationship to nivolumab = yes AND relationship to regorafenib = no
- Related to Both: relationship to regorafenib = yes AND relationship to nivolumab = yes
- Any related: relationship to regorafenib = yes OR relationship to nivolumab = yes

Descriptive summary tables (frequency and percentage of patients, not of events) will be presented using the most recent version of MedDRA terminology, for the following:

- Overview over treatment-emergent AEs
- Treatment-emergent AEs with grade 3, 4, or 5
- Treatment-emergent AEs by worst CTCAE grade
- Treatment-emergent AEs occurring in at least 5% of patients

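### SAP 6.5.2: the per-drug related-AE rows leave out events attributed to both drugs, and the patient counts in general only bound each drug's inclusive rate

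*SAP*

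**What the plan says.** SAP 6.5.2 sets the scope in one sentence. The breakdown applies to every treatment-emergent AE table "except the one displaying (S)AE by relationship, will also be broken out by relationship to drug (Rego/Novo/Both". Four categories follow, each defined at event level:

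- The regorafenib category takes events attributed to that drug alone: "Related to Rego: relationship to regorafenib = yes AND relationship to nivolumab = no".
- The nivolumab category is its mirror image and again shuts out shared events: "Related to Nivo: relationship to nivolumab = yes AND relationship to regorafenib = no".
- Shared events form a third category of their own: "Related to Both: relationship to regorafenib = yes AND relationship to nivolumab = yes".
- The fourth category is the union of the other three: "Any related: relationship to regorafenib = yes OR relationship to nivolumab = yes".

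The unit of counting is the patient: "Descriptive summary tables (frequency and percentage of patients, not of events".

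On the data side, Protocol 10.3.3 requires the investigator to document for each AE or SAE that he or she "has provided an assessment of causality for both, regorafenib and nivolumab". Protocol 6.6 says that "some drug-related AEs such as diarrhea, abnormal thyroid function, and fatigue are overlapping". SAP 4.1 provides subject listings of everything in the database. The SAP does not define the layout of the exempt (S)AE-by-relationship table.

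**The concern.** The labels 'Related to Rego' and 'Related to Nivo' carry no word such as 'only', yet each drops every event that the investigator attributed to both drugs. None of the four categories counts patients with at least one event related to a given drug whatever was recorded for the other. A reader looking for how many patients had a regorafenib-related AE would naturally go to the row labelled that way and could take away too low a figure.

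The obvious repair, adding the single-drug row to the 'Both' row, is unsafe in a table of patients. One patient may have a regorafenib-only event and a separate event rated as related to both, and is then counted twice.

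The stake is the descriptive safety picture for each component. The breakdown extends to the tables by worst grade, withdrawal, dose reduction and interruption. Protocol 6.6.1 and 6.6.2 let the two drugs be modified independently when a toxicity is clearly attributable to one of them, so per-drug figures are of practical interest.

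**Working it through.** The plan states no figure on this point, so there is nothing to reproduce. The check is a set argument followed by illustrations. 'Row' below means the category however it is displayed, because the SAP shows no table shells.

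**Inputs.** The four definitions and the patient-level counting come from SAP 6.5.2. The denominator of 70 treated patients comes from SAP 6.2.1. All AE counts and rates below are assumed, because the documents give none.

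**Notation.** For a given kind of event (any TEAE, one preferred term, or events at or above a given grade), let R, N and B be the numbers of patients with at least one regorafenib-only, nivolumab-only and both-related event. Any is the number with at least one related event. T is the number with at least one regorafenib-related event, inclusive of events also attributed to nivolumab.

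**Direction.** Every patient in R is in T, so R ≤ T and the row cannot overstate. T exceeds R exactly when some patient has a both-related event and no regorafenib-only event.

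**Bounds.**

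- Every patient in B is in T, so T ≥ B.
- A patient in Any but not in T has only nivolumab-only events, so Any − T ≤ N and T ≥ Any − N.
- Every patient in T is in R or B, so T ≤ R + B. Also T ≤ Any.

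Hence max(R, B, Any − N) ≤ T ≤ min(R + B, Any). Exchanging R and N gives the bounds for nivolumab. Integer programming over the seven possible event patterns per patient gave the same limits in all four count sets tried.

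**Three of these count sets (assumed), n = 70.**

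| R, N, B, Any | Drug | Row shows | Inclusive count can be |
|---|---|---|---|
| 30, 15, 35, 60 | regorafenib | 30 (42.9%) | max(30, 35, 45) = 45 to min(65, 60) = 60 (64.3% to 85.7%) |
| 30, 15, 35, 60 | nivolumab | 15 (21.4%) | max(15, 35, 30) = 35 to min(50, 60) = 50 (50.0% to 71.4%) |
| 10, 5, 5, 15 | regorafenib | 10 (14.3%) | max(10, 5, 10) = 10 to min(15, 15) = 15 (14.3% to 21.4%) |
| 20, 10, 10, 40 | regorafenib | 20 (28.6%) | max(20, 10, 30) = 30 to min(30, 40) = 30 (exactly 42.9%) |

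In the first set R + B = 65 exceeds Any = 60, so simple addition is visibly wrong. In the second the row may already equal the inclusive figure. In the last, R + N + B = Any, so no patient is in two categories and the inclusive figure is recovered exactly.

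**Size under an assumed model.** Take independent Poisson event counts with mean m AEs per patient, split 40% regorafenib only, 10% nivolumab only, 30% both and 20% unrelated. The chance of at least one event in a group with share s is 1 − exp(−m·s). The inclusive shares are 0.40 + 0.30 = 0.70 for regorafenib and 0.10 + 0.30 = 0.40 for nivolumab.

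| m | Regorafenib row, s = 0.40 | Inclusive, s = 0.70 | Nivolumab row, s = 0.10 | Inclusive, s = 0.40 |
|---|---|---|---|---|
| 0.1 | 3.9% | 6.8% | 1.0% | 3.9% |
| 0.8 | 27.4% | 42.9% | 7.7% | 27.4% |
| 5 | 86.5% | 97.0% | 39.3% | 86.5% |

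Adding the regorafenib and 'Both' rows behaves as follows:

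- At m = 0.1, 3.9% + 3.0% gives 6.9% (6.88% unrounded) against a true 6.8%, which is almost exact.
- At m = 0.8, 27.4% + 21.3% = 48.7% against 42.9%, about 6 points too high.
- At m = 5, 86.5% + 77.7% exceeds 100% and is useless.

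**The case against.** The exclusive split is a legitimate display and is openly defined. Protocol 6.6 lets the investigator assign a toxicity to one drug alone or to the pair, and expects some toxicities to belong mainly to one drug. The three exclusive categories mirror that scheme. At event level they partition the related events, so no related event is lost. The safety objective concerns the combination, and Protocol 9.4.5 asks for TEAEs by relation to study treatment, which the any-related category supplies. Safety is descriptive throughout. On this view the complaint is about labels and one extra row.

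Most of that stands, and it limits the point. It does not remove it: a definition in the SAP does not put the inclusive count in the table, and an unqualified label invites the wrong reading.

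A reader might go further and infer that each drug's related-AE rate is certainly understated, or that it is lost. The documents support neither:

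- Understatement needs at least one patient whose only events related to that drug are rated as related to both. The protocol's list of overlapping toxicities makes this plausible, but no rate is given.
- The inclusive rates can be obtained from the database or the subject listings.
- The exempt (S)AE-by-relationship table might show them, since its layout is undefined.
- For a single preferred term with low incidence, adding the two rows may be close enough.

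**Conclusion.** The point holds for the tables that SAP 6.5.2 breaks out by relationship. As specified, the two single-drug rows omit shared events, no inclusive per-drug row is planned, and the published patient counts in general give only a range for the inclusive rate. The bias, if present, has one direction: downward.

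Its size in this trial is unknown. In the assumed scenarios the regorafenib shortfall runs from about 3 points (m = 0.1) through about 16 (m = 0.8) to about 11 (m = 5). For nivolumab it runs from about 3 through about 20 to about 47. These figures rest on the assumed 40/10/30/20 split and on independent Poisson counts, and they illustrate the mechanism rather than forecast the result.

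This is a reporting defect in descriptive safety tables. It is worth correcting because the correction is cheap and the data are already collected. The any-related rates and the test of ORR are untouched.

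**What to change.** In SAP 6.5.2, add one inclusive row per drug: relationship to regorafenib = yes whatever the nivolumab assessment, and relationship to nivolumab = yes whatever the regorafenib assessment. Rename the present exclusive rows 'regorafenib only' and 'nivolumab only'. Keep 'Both' and 'Any related' as they are. While editing, define the categories of the exempt (S)AE-by-relationship table and correct 'Novo' in the scope sentence.

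The cost is two extra rows per table and two relabelled ones. Causality is already recorded for each drug, so no new data are needed and no planned output is lost.
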